4.6.3.10. Renal Safety

Laboratory measures related to renal safety will be analyzed as specified for laboratory measurements in Section 4.6.5.

In addition, 2 shift tables examining renal function will be created. A minimum-to-minimum shift table of estimated glomerular filtration rate estimated by the Chronic Kidney Disease Epidemiology Collaboration equation with units mL/min/1.73 m², using categories (<30, ≥30 to <45, ≥45 to <60, ≥60 to <90, and ≥90 mL/min/1.73 m²). A maximum-to-maximum shift table of UACR, using the categories UACR <30 mg/g, ≥30 mg/g UACR to ≤300 mg/g, UACR >300 mg/g (respectively, these represent normal, microalbuminuria, and macroalbuminuria).

MMRM analyses as described in Section 4.6 for estimated glomerular filtration rate and log-transformed UACR will be provided. Log transformation will be performed for UACR.

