PROMIS Short Form v1.0 Sleep Disturbance 8b	X		X		X		X				X	X			
PROMIS Short Form v1.0 Sleep-related Impairment 8a	X		X		X		X				X	X			
SF-36v2, acute	X						X				X	X			
PHQ-9	X	X					X				X	X			The PHQ-9 should be administered after assessment of AEs, if both collected on the same day. PHQ-9 at V7 and V11 may be scheduled for any day +/- 14 days.
Clinician-Administered Assessments (Paper)															
C-SSRS screening/baseline	X														The C-SSRS should be administered after assessment of AEs, if both collected on the same day. The C-SSRS since last visit is adapted for the assessment of the ideation and behavior categories only. The Intensity of Ideation and Lethality of Behavior sections are removed.
C-SSRS (since last visit version)		X					X				X	X			
Laboratory Tests and Sample Collections															

	Study Period I - Screening	Study Period II - Treatment												Study Period III - Post-Treatment Follow-up	Comments
		2	3	4	5	6	7	8	9	10	11	ED			
Visit number	1												801		
Weeks from randomization	-4	0	4	8	12	16	20	24	36	48	52	-	See footnote a		
Visit interval tolerance (days)	-14 to +21	-	±3	±3	±3	±3	±7	±3	±7	±3	±7	±7	±3		
Fasting Visit		X	X	X	X	X	X	X	X	X	X	X		See footnote b.	
Hematology	X				X			X	X		X	X	X		
HbA1c	X	X			X			X	X		X	X	X		
Clinical chemistry (includes glucose)	X	X			X			X	X		X	X	X		
Lipid panel		X						X			X	X	X		
hsCRP		X						X			X	X			
Serum pregnancy	X													Only for WOCBP and females with a history of tubal ligation. See Section 10.4, Appendix 4.	
Urine pregnancy (local)		X			X			X	X		X	X		A urine pregnancy test must be performed at V2 with the result available prior to first dose/injection of study intervention for WOCBP only. Additional pregnancy tests (beyond those required per the SoA) should be performed at any time during the trial if a menstrual period is missed, there is clinical suspicion of pregnancy, or as required by local law or regulation.	
FSH	X													Optional; performed as needed to confirm postmenopausal status. See Section 10.4, Appendix 4.	
Insulin		X						X			X	X	X		
C-Peptide		X						X			X	X	X		
Free fatty acids		X						X			X	X	X		

	Study Period I - Screening	Study Period II - Treatment												Study Period III - Post-Treatment Follow-up	Comments
		2	3	4	5	6	7	8	9	10	11	ED			
Visit number	1												801		
Weeks from randomization	-4	0	4	8	12	16	20	24	36	48	52	-	See footnote a		
Visit interval tolerance (days)	-14 to +21	-	±3	±3	±3	±3	±7	±3	±7	±3	±7	±7	±3		

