Fasting Visit		X	X	X	X	X	X	X	X	X	X	X		See footnote b.	
Cystatin-C	X							X			X	X	X		
Calcitonin	X										X	X	X		
Pancreatic amylase	X				X			X			X	X	X		
Lipase	X				X			X			X	X	X		
TSH	X														
eGFR	X	X			X			X	X		X	X	X	Calculated using CKD-EPI method.	
UACR	X	X			X			X	X		X	X	X		
PK samples		X	X		X			X			X	X	X	PK samples to be collected predose and close to ADA samples.	
Immunogenicity (ADA) samples		X	X		X			X			X	X	X	In the event of systemic drug hypersensitivity reactions (immediate or nonimmediate), additional unscheduled samples should be collected as detailed in Section 10.3.7.2 (Hypersensitivity Reactions). Immunogenicity samples and PK samples for immunogenicity must be predose.	
Stored Samples															
Genetics sample		X												Sample can be obtained at or after the specified visit.	
Exploratory biomarker samples		X						X			X	X	X		
Randomization and Dosing															
Register visit with IWRS	X	X	X	X	X	X	X	X	X	X	X	X	X		

	Study Period I - Screening	Study Period II - Treatment												Study Period III - Post-Treatment Follow-up	Comments
		2	3	4	5	6	7	8	9	10	11	ED			
Visit number	1												801		
Weeks from randomization	-4	0	4	8	12	16	20	24	36	48	52	-	See footnote a		
Visit interval tolerance (days)	-14 to +21	-	±3	±3	±3	±3	±7	±3	±7	±3	±7	±7	±3		
Fasting Visit		X	X	X	X	X	X	X	X	X	X	X	X	See footnote b.	
ISA assignment via IWRS	X														
ISA treatment randomization via IWRS		X													
Observe participant administer study intervention		X												Participants should administer their first dose of study intervention at the end of the V2, after other study procedures are completed.	
Dispense study drug via IWRS		X	X	X	X	X	X	X	X	X					
Dispense study drug to participant (for at home dosing)		X	X	X	X	X	X	X	X	X					
Dispense ancillary supplies to participant		X												Dispensation of ancillary supplies may vary beyond V2 based on expiry dating of applicable supplies and/or participant needs.	
Participant returns all unused study intervention			X	X	X	X	X	X	X	X	X	X			
Assess study intervention compliance			X	X	X	X	X	X	X	X	X	X			

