#### **4.3. Justification for Dose**

Tirzepatide doses of up to 15 mg administered SC QW will be evaluated in this study. Participants may be treated with lower maintenance dose of 10 mg if they do not achieve full dose escalation to 15 mg and/or do not tolerate 15 mg.

These doses and associated escalation schemes were selected based on assessment of safety, efficacy (weight loss), and GI tolerability data in Phase 1, 2, and 3 studies in patients with T2DM, followed by exposure-response modeling of the data that predicted weight loss in patients with overweight or obesity.

Dosing algorithms starting at a low dose of 2.5 mg accompanied by dose escalation of 2.5 mg increments every 4 weeks should permit time for development of tolerance to GI events and are predicted to minimize GI tolerability concerns.

Similar to the GLP-1RA class, most of the tirzepatide AEs were dose-dependent and GI-related, consisting mainly of nausea, vomiting, and diarrhea. In general, these events were mild or moderate in severity, with few severe episodes, and transient.

Tirzepatide doses of 10 mg and 15 mg as MTD were selected based principally on the following criteria:

- each dose provides robust weight loss relative to placebo
- the percent of participants achieving  $\geq 10\%$  weight loss is higher with 15 mg than 10 mg, and
- safety and tolerability were supported by Phase 3 results in T2DM.

The proposed tirzepatide maintenance dose of up to 15 mg using a dose-escalation regimen is expected to safely maximize the potential for weight loss while minimizing GI tolerability concerns as has been achieved for approved GLP-1 RA drugs. The subsequent benefit of weight loss should result in clinically meaningful improvements in AHI.

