4.6.5. Clinical Laboratory Evaluation

Limits from the performing laboratory will be used to define low (L) and high (H). Descriptive summaries by treatment and by nominal visit will be provided for the baseline and postbaseline values as well as the change from baseline values. The associated descriptive will be presented in International System of Units and in conventional units.

For selected laboratory analyte measurements collected quantitatively, observed, and change from baseline values for each visit may be displayed in plots for participants who have both a baseline and at least 1 postbaseline planned measurement. Unplanned postbaseline measurements will be excluded from plots.

A shift table will be provided including unplanned measurements. The shift table will include the number and percentage of participants within each baseline category (low, normal, high, or missing) versus each postbaseline category (low, normal, high, or missing) by treatment. The proportion of participants shifted will be compared between treatments using Fisher's exact test.

For qualitative laboratory analytes, the number and percentage of participants with normal and abnormal values will be summarized by treatment.

A listing of abnormal findings will be created for laboratory analyte measurements, including qualitative measures. The listing will include:

- participant identification
- treatment group
- laboratory collection date
- study day
- analyte name, and
- analyte finding.

The MMRM model or ANCOVA (if MMRM model is not applicable) as described in Section 4.6 will be used for the analysis during the treatment period (excluding the safety follow-up period) for the continuous measurements for selected laboratory tests with or without log-transformed (postbaseline measure/baseline measure) response variables. For measures analyzed using log-transformed values, the results will be presented with the scale back transforming to the original, related scale.

The summary of treatment-emergent abnormal, high, or low laboratory results any time will be provided.

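### The planned eGFR analyses appear to rest on creatinine alone, so greater muscle loss on tirzepatide could partly or fully mask a fall in filtration; the cystatin C already collected is not used for an eGFR check

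*SAP*

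**What the plan says.** SAP 4.6.3.10 plans two analyses of eGFR. One is "A minimum-to-minimum shift table of estimated glomerular filtration rate estimated by the Chronic Kidney Disease Epidemiology Collaboration equation", with category limits at 30, 45, 60 and 90. The other is a model: "MMRM analyses as described in Section 4.6 for estimated glomerular filtration rate and log-transformed UACR will be provided". The protocol's Schedule of Activities says of eGFR only "Calculated using CKD-EPI method", and the laboratory list in Protocol Appendix 2 likewise gives CKD-EPI without a marker.

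Other renal outputs are planned. The same SAP section has "A maximum-to-maximum shift table of UACR, using the categories UACR <30 mg/g" and higher bands, and a log-UACR MMRM. Sections 4.6.3.10.1 and 4.6.3.10.2 deal with acute renal and dehydration events. The section also states: "Laboratory measures related to renal safety will be analyzed as specified for laboratory measurements in Section 4.6.5". Section 4.6.5 then promises: "Descriptive summaries by treatment and by nominal visit will be provided for the baseline and postbaseline values as well as the change from baseline values". Protocol 9.3.5.5 adds a comparison of central laboratory values and changes between the arms at each scheduled visit.

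The Schedule of Activities includes cystatin C, and Appendix 2 lists it under additional testing. The SAP never mentions it, and neither document plans an eGFR derived from it.

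**The concern.** Serum creatinine depends on how much is generated, mainly by muscle, as well as on how fast the kidney clears it. The trial compares a drug chosen because "each dose provides robust weight loss relative to placebo" with placebo, and percent change in body weight is a key secondary endpoint. If part of the extra weight lost is muscle, creatinine generation falls more in the tirzepatide arm, and creatinine-based eGFR rises there without any change in filtration. This shift arises after randomization, so adjusting for baseline does not remove it.

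At stake is a between-arm safety comparison. SAP 4.6.3.10.1 itself raises the possibility that severe gastrointestinal events, through dehydration, harm renal function. Participants with eGFR down to 30 are eligible (exclusion criterion 21), so some may enter with limited reserve. A real decline could look smaller than it is, or be absent from the eGFR displays.

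**Working it through.** The plan states no figure on this point, so there is nothing to reproduce. The check compares schedules and then applies simple algebra with assumed inputs.

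**1. Which marker?** The Schedule of Activities gives the following; creatinine belongs to the chemistry panel, the row that begins "Clinical chemistry (includes glucose".

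| Time point | eGFR | Chemistry (creatinine) | Cystatin C |
|---|---|---|---|
| Visit 1 (Week -4) | yes | yes | yes |
| Visit 2 (Week 0) | yes | yes | no |
| Visit 5 (Week 12) | yes | yes | no |
| Visit 8 (Week 24) | yes | yes | yes |
| Visit 9 (Week 36) | yes | yes | no |
| Visit 11 (Week 52) | yes | yes | yes |
| ED | yes | yes | yes |
| 801 | yes | yes | yes |

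All 8 eGFR time points have creatinine; 3 of the 8 have no cystatin C. An eGFR reported at all eight cannot use cystatin C throughout. Creatinine is a strong inference, but it is not stated.

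**2. Model (assumption, not from the documents).** At steady state, creatinine is proportional to generation divided by GFR, and eGFR is proportional to creatinine^(-b). Let generation fall by a fraction g and true GFR by a fraction d. The ratio of follow-up to baseline eGFR is

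R = ((1 - g) / (1 - d))^(-b).

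I take b = 1.0 to 1.2 at higher creatinine and b = 0.25 to 0.30 at low creatinine, where the equation is flatter. These exponents are assumptions.

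**3. No true change (d = 0).** R = (1 - g)^(-b).

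| Fall in generation | eGFR rise, b = 1.0 to 1.2 | eGFR rise, b = 0.25 to 0.30 |
|---|---|---|
| 2% | 2.0% to 2.5% | 0.5% to 0.6% |
| 5% | 5.3% to 6.3% | 1.3% to 1.6% |
| 10% | 11.1% to 13.5% | 2.7% to 3.2% |

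For the categories, take a participant at eGFR 57 with unchanged filtration and b = 1.0 to 1.2. The reading becomes 58.2 to 58.4, 60.0 to 60.6, or 63.3 to 64.7 for the three rows. The last two reach the 60 limit.

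**4. Full masking.** R = 1 when g = d, whatever b is. A 2%, 5% or 10% fall in generation therefore offsets a true GFR fall of 2%, 5% or 10%.

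**5. Partial masking.** With d = 10% and g = 5%, R = (0.95/0.90)^(-b), an apparent change of -5.3% (b = 1.0) to -6.3% (b = 1.2). With g = 0 it would be 0.90^b, that is -10.0% to -11.9%.

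**6. What else could show the decline?**
- UACR measures albumin excretion, not filtration.
- The acute renal event summary is optional and tied to an overall count above 10; a modest decline need not be reported as an event.
- Raw cystatin C falls under SAP 4.6.5 (summaries by visit, low/normal/high shifts, modelling only for selected tests) and Protocol 9.3.5.5. It is not put on the eGFR scale or in the renal categories, and nothing asks for it to be read beside eGFR.

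**The case against.** The strongest reply is that much of this is already covered. Renal laboratory measures go to SAP 4.6.5, whose shift table is compared between arms by Fisher's exact test, and Protocol 9.3.5.5 commits to comparing central laboratory measures by arm and visit. A rise in cystatin C on tirzepatide could appear there. This stands, and it narrows the gap to two things: cystatin C is not named, and it is not converted to eGFR.

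Second, a reader might infer that creatinine eGFR is the plan's only look at the kidney. The documents do not support that: UACR has its own shift table and MMRM, and renal and dehydration events are addressed.

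Third, a reader might infer that the bias is certain and always flatters tirzepatide. It is conditional on differential muscle loss. Neither document gives a lean-mass or creatinine figure, and both arms are advised an energy deficit of about 500 kcal/day and more exercise, which may reduce the contrast. It need not vanish, since superior weight loss over placebo is what the trial sets out to show.

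Fourth, a reader might apply the exponent to the artefact alone and conclude that the masked fall exceeds g. The exponent acts on the true fall too, so the offset is one for one.

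Last, cystatin C is not drawn between Visit 1 and Week 24, while escalation takes 20 weeks. For participants who stay in the study, a cystatin C eGFR says nothing about that period. This limits the remedy but does not remove the case for it at Weeks 24 and 52.

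**Conclusion.** The point holds as a worthwhile improvement to a safety analysis. The only prespecified eGFR analyses leave the marker unnamed, and the schedule implies creatinine. If tirzepatide participants lose more muscle, those analyses are biased towards apparently better renal function, and a g% fall in creatinine generation offsets a g% true fall in GFR. This rests on the steady-state model and on the premise that generation follows muscle mass.

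The size in this trial cannot be computed from the documents. At low creatinine the artefact is small in absolute terms (0.5% to 3.2% for falls of 2% to 10% under the assumed exponents). The documents do not support saying that a decline will be hidden, or that cystatin C goes unanalysed. No efficacy or error-controlled conclusion is affected.

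**What to change.** In SAP 4.6.3.10:
- State that the main eGFR uses the creatinine CKD-EPI equation, and name the version.
- Add a sensitivity analysis of eGFR by a CKD-EPI cystatin C or combined equation, fixing the choice before unblinded renal data are seen. A combined equation keeps part of the creatinine artefact.
- Analyse change from the Visit 1 baseline at Weeks 24 and 52 by MMRM, and give a category shift table on the available draws (Visit 1, Week 24, Week 52, ED, 801).
- Present these beside creatinine eGFR.

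The cost is one derived variable and two repeated outputs, with no new samples. There are downsides. Five time points replace eight, with one scheduled baseline draw instead of two, so the shift table will not match the creatinine one exactly. It gives no help during dose escalation. Cystatin C also has influences other than GFR, so neither marker should stand alone.

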4.6.3.10.1. Acute Renal Events

Because severe GI events may lead to dehydration, which could cause a deterioration in renal function including acute renal failure, dehydration events will be analyzed as described in the next section. Acute renal events associated with chronic renal failure exacerbation will also be captured.

Severe/serious renal events from the following SMQ search will be considered as AESI.

The counts and percentages of participants with acute renal events may be summarized by treatment if overall count >10 by using the MedDRA PTs contained in any of the following SMQs:

- Acute renal failure: narrow terms in *Acute renal failure* SMQ (20000003), and
- Chronic kidney disease: narrow terms in *Chronic kidney disease* SMQ (20000213).

In addition, a listing of participants with treatment-emergent acute renal events may be provided, if deemed necessary.

4.6.3.10.2. Dehydration

Dehydration events will be captured in the narrow terms in *Dehydration* SMQ (20000232). Severe/serious dehydration events will be considered as AESI. A listing of participants with treatment-emergent dehydration events may be provided.

4.6.3.11. Thyroid Safety Monitoring

4.6.3.11.1. Calcitonin

The purpose of calcitonin measurements is to assess the potential of tirzepatide to affect thyroid C-cell function, which may indicate development of C-cell hyperplasia and neoplasms.

Observed calcitonin data (a thyroid-specific laboratory assessment) will be summarized by treatment and nominal visit.

The counts and percentages of participants with a maximum postbaseline calcitonin value in the following thresholds will be provided by treatment and maximum baseline calcitonin value (≤ 20 ng/L, > 20 ng/L to ≤ 35 ng/L, > 35 ng/L). Postbaseline categories are:

- ≤ 20 ng/L
- > 20 ng/L to ≤ 35 ng/L
- > 35 ng/L to ≤ 50 ng/L
- > 50 ng/L to ≤ 100 ng/L, and
- > 100 ng/L.

4.6.3.11.2. C-Cell Hyperplasia and Thyroid Malignancies

Treatment-emergent thyroid malignancies and C-cell hyperplasia will be considered as AESI. Thyroid malignancies and C-cell hyperplasia will be identified using MedDRA HLT for *Thyroid neoplasms* and PT for *Thyroid C-cell hyperplasia*.

The counts and percentages of participants with treatment-emergent thyroid C-cell hyperplasia and malignancies may be summarized or a listing of participants with treatment-emergent thyroid C-cell hyperplasia and neoplasms may be provided if deemed necessary.

4.6.3.12. Treatment-Emergent Arrhythmias and Cardiac Conduction Disorders

Severe/serious treatment-emergent arrhythmias and cardiac conduction disorders will be considered as AESI. The cardiovascular events will include clinically relevant rhythm and conduction disorders.

The treatment-emergent arrhythmias and cardiac conduction disorder events will be identified using the MedDRA PTs. Detailed searching criteria can be found in Appendix 2 (Section 6.2).

The counts and percentages of participants with treatment-emergent arrhythmias and cardiac conduction disorders may be summarized by treatment and PT nested within SMQ. The PT will be ordered with decreasing frequency in tirzepatide arm within SMQ. A listing of participants with treatment-emergent arrhythmias and cardiac conduction disorders may be provided if deemed necessary.

4.6.3.13. Treatment-Emergent Malignancy

The malignancy events will be included using the MedDRA PTs contained in the *Malignant tumours* SMQ (20000194) narrow scope or *Tumours of unspecified malignancy* SMQ (20000195) narrow scope. Malignancy will be considered as an AESI.

The counts and percentages of participants with treatment-emergent malignancy will be summarized by treatment.

4.6.3.14. Abuse Liability

To identify AE terms suggestive of abuse liability potential, narrow terms from the *Drug abuse and dependence* SMQ (20000101) will be used. The counts and percentages of participants will be summarized by treatment group in order of decreasing frequency.

These analyses will be performed for individual CSRs and the summary of clinical safety.

4.6.4. Vital Signs

In the case that multiple records of an individual vital sign are collected at the same visit, they will be averaged prior to being used for data summaries and analyses.

Descriptive summaries by treatment and by nominal visit will be provided for baseline and postbaseline values as well as change from baseline values.

An MMRM and/or an ANCOVA model, as discussed in Section 4.6, using data including from the safety follow-up period might be conducted if necessary.

Counts and percentages of participants with treatment-emergent abnormal sitting SBP, sitting diastolic blood pressure, and pulse at any time during the entire study (including the off-drug follow up time period) will be summarized by treatment for participants who have both baseline and at least 1 postbaseline result. A treatment-emergent high result is defined as a change from a value less than or equal to the high limit at baseline to a value greater than the high limit at any time that meets the specified change criteria during the postbaseline period. A treatment-emergent low result is defined as a change from a value greater than or equal to the low limit at baseline to a value less than the low limit at any time that meets the specified change criteria during the postbaseline period. To assess decreases, change from the minimum value during the baseline period to the minimum value during the postbaseline period will be used. To assess increases, changes from the maximum value during the baseline period to the maximum value during the postbaseline period will be used. Both planned and unplanned measurements will be included in the analysis. The criteria for identifying participants with treatment-emergent vital sign abnormalities are stated in [Table GPIF.4.10](#).

Table GPIF.4.10. Categorical Criteria for Abnormal Treatment-Emergent Blood Pressure and Pulse Measurements

| Parameter | Low | High |
|---|--|---|
| Systolic BP (mm Hg) (supine or sitting – forearm at heart level) | ≤ 90 and decrease from baseline ≥ 20 | ≥ 140 and increase from baseline ≥ 20 |
| Diastolic BP (mm Hg) (supine or sitting – forearm at heart level) | ≤ 50 and decrease from baseline ≥ 10 | ≥ 90 and increase from baseline ≥ 10 |
| Pulse (bpm) (supine or sitting) | < 50 and decrease from baseline ≥ 15 | > 100 and increase from baseline ≥ 15 |

Abbreviations: BP = blood pressure; bpm = beats per minute

